MUSE Device to Improve Sleep Quality in Midlife Women

NCT05972486

31January2024

IRB Minimal Risk Protocol Template

General Study Information

Principal Investigator: [name], PA-C

Co- Principal Investigator: [name], DNP

Co- Investigator: [name]

Lead Coordinator: [name]

Study Title: MUSE Device to Improve Sleep Quality in Midlife Women

Protocol version number and date: V4 01/31/2024

Research Question and Aims

Hypothesis:

We hypothesize that the daily use of the Muse-S headband system will be an effective strategy for improving the sleep quality in peri- and postmenopausal women. We anticipate that the women who utilize the Muse-S headband will have improvements in time to sleep onset and sleep maintenance. We also anticipate a positive correlation between duration and frequency of use of the device and the improvement in sleep quality.

Aims, purpose, or objectives:

1. To obtain preliminary evidence regarding the feasibility of using the Muse-S headband system for management of sleep disturbances in peri- and postmenopausal women.
2. To obtain preliminary data on the effectiveness of the Muse-S headband system for management of sleep disturbances in peri- and postmenopausal women and to ascertain whether duration of treatment impacts efficacy.
3. To obtain preliminary data on the effectiveness of the Muse-S headband system in improving secondary outcomes of sleep quality including stress levels, mood and sexual function.

The overarching purpose of this study is to obtain preliminary evidence regarding the efficacy of the Muse-S headband system for management of sleep disturbances (insomnia and sleep disruption) in midlife women. This goal will be achieved with the following specific aims:

Objectives: The overarching goal of this project is to test the feasibility and efficacy of the Muse-S™ Headband, an electroencephalographic device, in management of sleep disturbances in midlife women.

Background:

Sleep problems (insomnia and sleep disruption) affect nearly half the women during the menopause transition and the postmenopausal years. The etiology of sleep disturbances in peri- and postmenopausal women is

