Behavioral interventions, specifically cognitive behavioral therapy, exercise, and mindfulness/relaxation have been shown to be safe and reasonably effective for management of insomnia and sleep disruption in midlife women. These are typically the first line interventions for management of sleep problems in midlife women. However, the evidence supporting the use of these interventions in midlife women is somewhat weak with a need for further research identified by the experts. Moreover, some of these interventions can be difficult to access, limiting their use. Women can also find it hard to engage in meditation. There is a need to study novel behavioral interventions for management of sleep disruption in midlife women that overcome some of the barriers with the existing treatment modalities. The Muse-S™ headband offers an opportunity to fill this gap by giving patients real time biofeedback with electroencephalogram (EEG) technology to guide them and build confidence in their abilities to incorporate meditation in their daily habits. Once calibrated to an individual, the Muse-S headband distinguishes between active and calm brain states to provide real time performance feedback. This is achieved by converting EEG signals, measured over the frontal and temporal cerebral cortices, into measures of the state of the brain (active versus calm). This biofeedback allows for real time reinforcement of successful meditation. Additionally, the device is portable and easily accessible to the public making it a viable behavioral therapy intervention for patients. The Muse-S headband is being used in studies in the division of General Internal Medicine on patients after breast cancer surgery, those with pain-related to fibromyalgia, and in healthcare providers who are experiencing stress.

The proposed study will assess the impact of the Muse-S headband on the sleep quality in peri-and postmenopausal women experiencing subjective sleep disturbances. The study will also evaluate the impact of the Muse-S headband on the secondary outcomes of mood, quality of life, stress, and sexual function. These

parameters are often negatively affected by poor sleep, and therefore improvement in sleep quality is likely to impact mood, anxiety, quality of life, stress and sexual function favorably.

Study Design and Methods

Methods:

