6-month (on-site visit /phone visit): Consists of a study coordinator visit at Menopause and Women's Sexual Health Center for a final weight, body mass index, blood pressure check and questionnaires for local participants. Participants that are not local or cannot make an on-site visit, questionnaires will be sent by email to be completed and a phone visit will be scheduled with study coordinator. **NOTE:** The PHQ 9 questionnaire will be reviewed at the time of the visit. If the score is severe (20-27) or the subject indicates suicidal ideation the investigators ([name] and [name]) will be notified and will discuss with the patient. If concern for active suicidal thoughts, the investigator will initiate immediate emergency evaluation. If severely depressed but no active thoughts of self-harm/plan, we will recommend an appointment with their PCP, EAP (if Mayo Employee) and offer the resource Psychology Today to help find a mental health provider.

Subject Information

Target accrual: 50 women

Subject population (adults):

This will be an open label single-arm clinical trial that will recruit **50 peri- and postmenopausal women** from the Menopause and Women's Sexual Health Clinic (MWSHC), Community Internal Medicine, Executive Health, or Family Medicine at Mayo Clinic, Rochester, who are identified as having significant sleep disturbance based on a standard questionnaire used for assessment of sleep quality and duration- the Pittsburgh Sleep Quality Index (PSQI). The PSQI is a 19-item questionnaire making up 7 clinically derived component scores. Each of the 7 clinically derived components is given a score from 0-3 to obtain a total score ranging from 0-21. Higher scores indicate worse sleep quality, with a **PSQI score >5 indicating poor sleep quality**.

Inclusion Criteria:

- Women between the ages of **45-65 years** (women in the menopause transition or in menopause, based on clinical assessment)
- **PSQI score >5**, with overall sleep quality rating of "fairly bad" or "very bad".

- Motivation VAS score equal to or greater than 5 with overall motivation rating of on a scale of 0-10 with 0 being not motivated at all and 10 being extremely motivated
- Access to an iPad, iPhone, or android device
- Have ability to provide informed consent

Exclusion Criteria:

- Suspected or untreated obstructive sleep apnea

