- Moderate to severe vasomotor symptoms warranting prescription medication use. The FDA categories for hot flash severity are classified as mild (sensation of heat without sweating), moderate (sensation of heat with sweating, able to continue activity), or severe (sensation of heat with sweating cause cessation of activity).
- Use of hormone therapy or hypnotic agents
- Use of supplements known to affect sleep
- A known, active, untreated clinically significant psychiatric condition
- Use of an investigational drug within 30 days of study enrollment or presence of a known history of any condition or factor judged by the investigator to preclude participation in the study or which might hinder adherence.
- Currently (within the past 3 weeks) been practicing mindfulness training on a weekly/regular basis

Potentially eligible participants will be identified from the MWSHC, Community Internal Medicine, Executive Health, or Family Medicine, where midlife women are evaluated for menopause and sexual health-related concerns. All the women seen in these areas will complete multiple questionnaires as part of their clinical evaluation, including the PSQI. They also complete questionnaires assessing mood (Patient Health Questionnaire 9, PHQ-9), anxiety (Generalized Anxiety Disorder 7, GAD-7), and sexual function (Female Sexual Function Index, FSFI and the Female Sexual Distress Score-Revised, FSDS-R), Quality of Life-LASA), Perceived Stress Scale (PSS) and Resilience- (CD-RS10).

Review of medical records, images, specimens

- The study involves data that exist at the time of IRB submission and data that will be generated after IRB submission. Include this activity in the Methods section.

Data Analysis**Data Analysis Plan:**

Demographic characteristics are described using mean and standard deviations or frequencies and percentages based on the type of variable. For the primary aims being the feasibility and efficacy of the MUSE device, descriptive statistics and graphical displays will be presented for data obtained on frequency and duration of use over the treatment time of six months. A linear mixed model with repeated measures for each time point that

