stress and sleep were taken. That information will be utilized to estimate the association between the average of time spent using the Muse-S with the stress and sleep level outcome. As secondary aim, the results of questionnaires for stress levels, mood and sexual function will be analyzed using the same linear mixed model with questionnaires being done at different intervals of the study to determine changes over time. Given the number of outcomes assessed, all analyses will be considered exploratory.

Endpoints:Primary Hypothesis:

- The regular use of the Muse headband will increase quality and quantity of sleep.

Secondary Hypothesis:

- The regular use of the Muse headband will decrease perceived stress levels, decrease anxiety, and improve sexual health.

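### Mood is measured only by the PHQ-9; if one of its nine items asks about sleep, part of any mood change may be the sleep outcome counted again, and no sensitivity analysis separates the two

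*Combined protocol and SAP*

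**What the plan says.** Aim 3 (Aims, purpose, or objectives) seeks preliminary data on the device's effectiveness in "improving secondary outcomes of sleep quality including stress levels, mood and sexual function". The Background gives the expected mechanism: "improvement in sleep quality is likely to impact mood, anxiety, quality of life, stress and sexual function favorably".

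The paragraph on identifying eligible women, after the Exclusion Criteria, assigns one construct to each instrument: "They also complete questionnaires assessing mood (Patient Health Questionnaire 9, PHQ-9), anxiety (Generalized Anxiety Disorder 7, GAD-7), and sexual function". The PHQ-9 is the only one labelled mood. The only PHQ-9 score described is a sum, in the safety instruction for the 6-month visit: "If the score is severe (20-27) or the subject indicates suicidal ideation".

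Under Inclusion Criteria, a woman must have a PSQI above 5 and must also rate her overall sleep quality in one of the two bad categories. For the secondary aim, the Data Analysis Plan states that "the results of questionnaires for stress levels, mood and sexual function will be analyzed using the same linear mixed model", to determine changes over time. It plans no item-level analysis, no PHQ-9 score without a sleep item and no second mood scale. It labels all analyses exploratory. The Secondary Hypothesis under Endpoints names stress, anxiety and sexual health, but not mood.

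**The concern.** Mood is listed as an outcome that should follow from better sleep. To show that, the mood measure has to be able to move separately from sleep. If one PHQ-9 item asks about sleep trouble, the total contains a piece of the sleep outcome. Because entry requires bad sleep, that item is likely to be raised at baseline. It can then fall when sleep improves for any reason, including natural change after selection on bad sleep, which a trial without a control arm cannot remove.

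What is at stake is how one result is read. A fall in the PHQ-9 could be reported as better mood, and as support for the pathway in the Background, when only the sleep item has moved. The same overlap would carry part of any association between Muse-S use and sleep into an association between use and mood. That second effect is conditional on use tracking sleep, and it is not quantified here.

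**Working it through.** The plan gives no power calculation, alpha, SD or expected PHQ-9 change, so there is no stated figure to reproduce. The check has two parts.

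**1. The cap, from the documents plus the item assumption**

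- Maximum score: 27, from the severe band at the 6-month visit.
- Nine items: 27 / 9 = 3 points per item.
- One item's share of the range: 3 / 27 = 11.1%. Score without it: 0 to 27 − 3 = 24.
- Assumed, not printed: exactly one of the nine items asks about sleep trouble.

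**2. How often a change confined to the sleep item would look like a change in the total**

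From the documents: n = 50 (target accrual). Assumed:

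- two-sided 0.05, counting only significant improvements;
- mean change of zero in the other eight items;
- SD of the eight-item change, s8, from 2.5 to 5;
- SD of the sleep-item change, ss = 0.9;
- correlation r between the two changes, from 0 to 0.4;
- a one-sample t test of mean change, as a simple stand-in for the mixed model.

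Formulas:

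- SD of total change = √(s8² + ss² + 2·r·s8·ss)
- SE = SD / √50
- noncentrality = d / SE, where d is the mean fall in the sleep item
- the share of significant trials then follows from the noncentral t distribution with 49 degrees of freedom.

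Most sensitive corner, s8 = 2.5 and r = 0:

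- SD = √(6.25 + 0.81) = 2.66; SE = 2.66 / 7.07 = 0.376.
- d = 0.5: 0.5 / 0.376 = 1.33, giving 26%.
- d = 1.0: 1.0 / 0.376 = 2.66, giving 74%.

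Least sensitive corner, s8 = 5 and r = 0.4:

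- SD = √(25 + 0.81 + 3.6) = 5.42; SE = 5.42 / 7.07 = 0.767.
- d = 0.5: 0.5 / 0.767 = 0.65, giving 9%.
- d = 1.0: 1.0 / 0.767 = 1.30, giving 25%.

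Share of trials with a nominally significant fall in the total:

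| s8 | r | d = 0.25 | d = 0.5 | d = 1.0 |
|---|---|---|---|---|
| 2.5 | 0 | 10% | 26% | 74% |
| 2.5 | 0.4 | 8% | 21% | 64% |
| 3.5 | 0 | 7% | 16% | 48% |
| 3.5 | 0.4 | 6% | 14% | 42% |
| 5 | 0 | 5% | 10% | 28% |
| 5 | 0.4 | 5% | 9% | 25% |

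At d = 0 the share is 2.5% in every row: no sleep-item change, no bias. The eight-item score also gives 2.5% throughout, but only because its true mean change was set to zero.

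**The case against.** **The premise is not printed.** No passage describes a PHQ-9 item on sleep, and a maximum of 27 says nothing about item content. This stands as a limit. The point rests on a declared assumption about a named instrument. The sponsor can check it by looking at its own form, and if it is wrong the point falls.

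**Poor sleep is itself a symptom of depression, and the documents present mood as downstream of sleep.** Both are fair. A reader might infer that the PHQ-9 total is invalid here, or that Aim 3 promises a mood effect independent of sleep. The documents support neither reading. They do expect sleep to act on mood, and the total alone cannot separate that effect from content shared by the two measures.

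**No decision is at risk.** The plan sets no alpha and no rule for claiming a mood benefit, calls everything exploratory, and leaves mood out of the Secondary Hypothesis. This also stands. A reader might take the percentages above as the plan's false-positive rate for mood. They are not: they count crossings of a threshold that the plan never sets, under assumed inputs. They show only how readily a change in one item can surface in the total.

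**Removing the item does not rescue the inference.** Correct. A reader might infer that a fall in the eight-item score would prove a mood benefit. The Subject population section states: "This will be an open label single-arm clinical trial". With no control arm, expectancy and natural change can move all nine items. Making the eight-item score a gate for any mood statement would also be too strict for an exploratory pilot.

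**Conclusion.** The concern holds as a minor point of interpretation. Mood rests on one instrument, in women selected for bad sleep, and nothing in the plan separates a change in mood from the sleep outcome counted again. If one PHQ-9 item concerns sleep, the overlap is at most 3 of 27 points. For a mean fall in that item of 0.5 points the illustrative chance of a nominally significant fall in the total is about 9-26%, and for 1.0 point about 25-74%. It is about 5-10% for 0.25 points and shows no excess when the item does not change. The SDs, the correlation, the size of the fall, the test and its level are all assumed. The primary aims are not affected.

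**What to change.** First confirm the item content on the study's own PHQ-9 form. Then add to the secondary-aim paragraph of the Data Analysis Plan, before the data are analysed:

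- The full PHQ-9 total remains the reported mood score, and its use in the safety review is unchanged.
- As a prespecified sensitivity analysis, the same linear mixed model is fitted to the PHQ-9 without its sleep item (0-24). The sleep item is summarised separately at baseline, 3 months and 6 months.
- If the total improves but the eight-item score does not, the report states that the change cannot be distinguished from the sleep outcome.
- If the eight-item score also improves, the report states that a single-arm, open-label trial still cannot attribute this to the device.

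The cost is a few sentences and one derived variable, provided that item responses are kept, with no new data and nothing further asked of participants. The downside is that the eight-item score is slightly less reliable and has no severity bands, so it should supplement the total and not replace it.

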All study participants will receive a new Muse-S headband system at study entry and will be asked to utilize it daily for a minimum of 10 minutes day for a period of 6 months (24 weeks). Three of the seven sessions per week will specifically be asked to be mind meditation.

The participants will be provided instructions on setting up the device and connecting it to their smart device. They will also receive general education on the different features of the Muse-S Headband. They will have access to specific education on meditation. They will also have access to sleep tools on their app.

The participants will complete the ASCQ-Me Sleep Impact-Short Form, Epworth Sleepiness Scale and Sleep Quality Assessment PSQI for evaluation of their sleep. In addition they will also completed the the Patient Health Questionnaire (PHQ-9), Generalized Anxiety Disorder Scale (GAD-7), Female Sexual Function Index (FSFI) and Female Sexual Distress Scale (FSDS-R), Quality of Life- (LASA), Perceived Stress Scale (PSS) and Resilience- (CD-RS10). Quality of Life, mood, anxiety, stress and sexual function are often negatively impacted by poor sleep.

The weight, body mass index and blood pressure will be obtained from the MWSHC, Community Internal Medicine, Executive Health, or Family Medicine visit data at 0 and 6 months.

The data will be recorded in REDCap at baseline, 3 months, and 6 months.

All study participants will have access to The Muse-S™ Headband system's customer service team based in Toronto, Canada, by telephone and email for assistance should they experience technical problems with the device.

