Server Data: As the subject completes any Muse-S sessions, the information from these sessions will be uploaded to the Muse-S ICloud servers hosted by Google. Each subject will be able to see their own data at the end of each session, and data from the previous session stored in the "me" tab in the app. Subject to the study organizers ensuring that the subjects have signed the appropriate consents, study organizers will have access to each subject's data to monitor compliance, performance and outcomes, but will not get access to Journal entry information (if subject chooses to write a Journal entry). These data that the study organizers will have access to may include the study-specific identification number, gender, and age of the subject, the session type, the time and duration of each session, EEG data, heart rate (PPG) data, and the performance per session. Interaxon's privacy policy, which can be found at

██████████ will apply to Interaxon's use of the subjects' data. To maximize protection of the individual's privacy, the study organizers will ensure that the subjects are assigned anonymized email address and names for use in the Muse -SÔ application and when contacting the Muse-SÔ customer support. To ensure that no health data is shared with Interaxon, the study organizers have agreed to ensure that no health data will be shared with Interaxon. At the end of the study, the data collected in Google ICloud Server associated with study email addresses will be deleted.

Subject Retention

Participants will not be remunerated for participating in this study, but they will be allowed to keep the Muse-S headbands.

Study Design

We will use standardized procedures to ensure uniform instructions and support for all subjects for the recruitment, screening, and study entry.

Recruitment:

Women that come to the Menopause and Women's Sexual Health Clinic (MWSHC), Community Internal Medicine, Executive Health or Family Medicine at Mayo Clinic Rochester, who are identified as having significant sleep disturbance based on a standard questionnaire used for assessment of sleep quality and duration- the Pittsburgh Sleep Quality Index (PSQI) score >5 are recruited to the study based on the inclusion/exclusion criteria. If the participant is interested in the study the clinician will notify the study coordinator of participants eligibility, study coordinator at that time will set up a designated time to sign consent and get the participant enrolled in the study.

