Participants will not be reimbursed for their time spent in the study, but all participants will be given the option of keeping the Muse-S™ Headband system for continued use post study participation.

Consent and Screening:

Study coordinator will meet with the potential participant who has expressed an interest in participating in the study. They will begin by introducing the study details, and after determining that the subject has continued interest in study participation, will move on to the study consent. If the subject chooses to consent, they will screen the participant for study entry inclusion/exclusion criteria. If the study entry criteria are met, the subject will begin their study participation. They will be asked to complete the study questionnaires.

Please note: Participants must have access to an iOS or Android capable device to take part in this study in order to interact with the Muse-S™ Headband system.

Treatment phase:

During the first three months of study, participants will be asked to complete the intervention portion of the study using the Muse-S™ headband. If the MUSE device is not being used at least 3x a week for 10 minutes a day, the participant may get a reminder email or a phone call to remind them to use the Muse-S™ headband

system. Participants will receive an email link at 90 days from REDCap to complete their questionnaires for the study. If not completed in a timely manner there will be reminders by email and/or phone to complete.

Study Follow-Up Visit:

The study will consist of follow up at 3 month and 6 months.

3 month (questionnaire only visit): questionnaires will be sent via email **NOTE:** once questionnaires are complete the study coordinator will check the PHQ 9 score the same day the participant completes the questionnaire via the electronic link. The coordinator will immediately notify the investigators if the score is severe or subject indicates suicidal ideation. The investigators will contact the patient immediately (same day) and if there is concern for active suicidal thoughts, they will recommend the patient pursue emergency evaluation (such as local ED or 988 suicide prevention hotline) or contact local authorities for a welfare check if the patient declines. If severely depressed but no active thoughts of self-harm/plan, we will recommend an appointment with their PCP, EAP (if Mayo Employee) and offer the resource Psychology Today to help find a mental health provider.

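### The mixed model for change over time names no missing-data method and does not say that recorded device use informs the mean change, so improvement may be overstated if lapsed users improve less and return fewer forms

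*Combined protocol and SAP*

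**What the plan says.** This is an "open label single-arm clinical trial" with "Target accrual: 50 women". On timing: "The data will be recorded in REDCap at baseline, 3 months, and 6 months".

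Under Data Analysis Plan, a linear mixed model with repeated measures is used to "estimate the association between the average of time spent using the Muse-S with the stress and sleep level outcome". Stress, mood and sexual function then "will be analyzed using the same linear mixed model with questionnaires being done at different intervals of the study to determine changes over time". The plan names no missing-data method, missingness assumption, analysis population, sensitivity analysis or expected dropout rate. It does not say whether use interacts with visit, or over whose use a mean change would be averaged.

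On data collection:
- **Month 3** (Treatment phase; Study Follow-Up Visit) is by emailed questionnaire. "If not completed in a timely manner there will be reminders by email and/or phone to complete".
- **Month 6** (Study Follow-Up Visit) is on site with the coordinator for local women. Others receive emailed forms and a scheduled phone visit.
- **Use** (Server Data) is uploaded as sessions are completed, separately from the forms. Subject to consent, the study team has each woman's "data to monitor compliance, performance and outcomes", which may include "the session type, the time and duration of each session". The server data are to be deleted when the study ends.

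The Hypothesis section expects more frequent and longer use to go with greater improvement in sleep.

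**The concern.** With one arm, the result is a within-woman change, and there is no control group in which selective non-return could partly cancel. A likelihood-based mixed model handles missing scores validly when missingness depends only on what is in the model. If it depends on use, and use also drives change, use must be allowed to act on the change. A main effect of use does not do this. It shifts a woman's level equally at all visits, baseline included, whereas the gap between users and stoppers opens only after baseline.

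At stake is a mean change weighted toward women who kept using the device but open to being read as the result for all 50. The aims are preliminary evidence of feasibility and effectiveness. If a later trial were sized on this estimate (an assumption), an effect 14% to 17% too large would give 1 − 1/1.14² = 23% to 1 − 1/1.17² = 27% too few participants.

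**Working it through.** The plan gives no effect size, SD, power or dropout figure, so there is no figure of its own to reproduce. From the documents come the 50 women, the single arm, the three visits and the hypothesised link between use and benefit. Everything else below is assumed.

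**Closed form.** Let p be the share who stop, Δu and Δs the improvement in users and stoppers, and mu and ms their chances of missing follow-up. Suppose both follow-up forms go missing together and baseline is unrelated to use. A visit-only model then has nothing with which to recover the missing change, and its large-sample estimate is the mean among returners:

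- R = (1 − p)(1 − mu) + p(1 − ms)
- overstatement = p(1 − p)(ms − mu)(Δu − Δs) / R

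Base case (p = 0.3, Δ = 3 and 1 PSQI points, missing 10% and 50%):

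- True change = −(0.7 × 3 + 0.3 × 1) = −2.40
- R = 0.63 + 0.15 = 0.78
- Estimate = −(0.63 × 3 + 0.15 × 1)/0.78 = −2.62
- Overstatement = 0.3 × 0.7 × 0.4 × 2/0.78 = 0.22, about 9% of 2.40

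Other cases:

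- Mild (p = 0.2; 3 and 1; 5% and 30%): 0.16 × 0.25 × 2/0.90 = 0.09
- Stoppers gain nothing (p = 0.3; 3 and 0; 10% and 50%): 0.21 × 0.4 × 3/0.78 = 0.32
- Extreme (p = 0.4; 3 and 0; 10% and 70%): 0.24 × 0.6 × 3/0.66 = 0.65
- Δu = Δs or mu = ms: zero
- Stoppers improve more (2 and 3; p = 0.3; 10% and 50%): 0.21 × 0.4 × (−1)/0.78 = −0.11, an understatement

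**Simulation of three models.** Unstructured covariance, PSQI SD 3, correlation 0.5, 200,000 women per scenario; 6-month change:

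| Scenario | True | Visit only | Plus use as main effect | Use-by-visit, averaged over all enrolled |
|---|---|---|---|---|
| Base | −2.40 | −2.62 | −2.59 | −2.47 |
| Base, half of those missing at 6 months have a 3-month score | −2.40 | −2.59 | −2.56 | −2.46 |
| Stoppers gain nothing | −2.10 | −2.42 | −2.37 | −2.20 |
| Extreme | −1.80 | −2.46 | −2.39 | −2.02 |
| Mild | −2.60 | −2.69 | −2.68 | −2.64 |
| Equal benefit | −3.00 | −2.99 | −2.99 | −2.99 |
| Equal missingness, 20% | −2.40 | −2.41 | −2.41 | −2.41 |
| Stoppers improve more | −2.30 | −2.18 | −2.19 | −2.25 |

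Where lapsed users improve less and return less, the overstatement is 0.09 to 0.66 with visit only, 0.08 to 0.59 with use as a main effect and 0.04 to 0.22 with use-by-visit. Some remains because average use is an imperfect, linear proxy for having stopped.

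**Precision.** In 600 base-case trials of 50 women, the estimate's SD was 0.50 (visit only), 0.50 (main effect) and 0.52 (use-by-visit).

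**A second set-up.** Random-intercept model, correlation 0.6, benefit rising with use, 400 trials of 50. With about 30% of 6-month forms missing, the truth was −1.50; visit only gave −1.59, main effect −1.57, use-by-visit −1.51. With 40% missing and a steeper slope, the truth was −1.49 and the models gave −1.75, −1.70 and −1.51. The first two are 0.26/1.49 = 17% and 0.21/1.49 = 14% too large.

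**Imputing from scores plus use.** With a true change of −2.40, visit only gave −2.58 and imputation with use −2.45. The share of bias removed is (0.18 − 0.05)/0.18, roughly 70%. Setting missing scores to baseline instead gives −(0.63 × 3 + 0.15 × 1) = −2.04 in the base case, an error in the other direction.

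**The case against.** Several stronger readings are tempting, and the documents do not support them.

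- *The model ignores use.* It does not. The plan relates average time of use to stress and sleep, and the secondary outcomes get the same model. A use-by-visit term would even suit Aim 2, on whether duration of treatment affects efficacy. What stands is that no such term is stated and nothing says use informs the mean change.
- *Women who stop are the likeliest not to return forms, so improvement is overstated.* No section links stopping to non-return, and the missingness rates above are assumptions. The protocol's hypothesis supports the direction but does not establish it.
- *All follow-up is by email.* This is true of month 3 only. The month-6 arrangements, the questionnaire reminders, the motivation threshold at entry, the exclusion for factors hindering adherence and the possible reminders for low use may all limit missingness.
- *Use is known for every woman.* Access depends on consent, and the accessible data are described only as what they may include.

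Two further objections have weight. Base-case bias (about 0.2) is under half the sampling SD (about 0.5), although a confidence interval does not reveal bias. The analyses are also declared exploratory, but because of the number of outcomes, which does not address missing scores. Finally, the hypotheses under Endpoints concern regular use. If regular users are the target population, the plan should say so; an analysis of whoever returns forms defines neither that group nor all enrolled women.

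**Conclusion.** The point holds in a conditional form. The plan estimates change from returned questionnaires, names no missing-data method, and states a role for device time only as an association with outcome level. If lapsed users improve less and return fewer forms, mean improvement may be overstated by about 0.1 to 0.3 PSQI points under moderate assumed missingness and 0.5 to 0.7 in an extreme case. Adding use only as a main effect removes little of this. The bias is nil if either benefit or missingness is unrelated to use, and changes sign if stoppers improve more.

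The sizes rest on assumed stopping rates, missingness and benefit, and are on the PSQI scale. On the stress, mood and sexual-function scales the bias would scale with the difference in improvement between users and stoppers. With no test threshold in the plan, the effect is on the estimate, not on an error rate. The change should be made because a better method is available at small cost, not because the trial would otherwise fail.

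**What to change.** Add a paragraph to the Data Analysis Plan that does the following:

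1. Analyses all enrolled women.
2. Lets server-recorded use inform missing 3- and 6-month scores, by one of two routes. Either multiply impute from the baseline score, the other follow-up score and use up to that visit, then fit the change-over-time model; or include a use-by-visit term and average the change over the use of all enrolled women.
3. Counts weeks with no sessions as zero use, and says what is done where a woman's server data are unavailable.
4. Requires per-woman use to be extracted before the server data are deleted at study end.
5. Reports questionnaire return rates by level of use at each visit, which is also a feasibility result.
6. Shows missing scores set to baseline, if at all, only as a pessimistic bound. Women enter on a PSQI score above 5, so baseline is selected to be high and is not a neutral no-change value.

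The cost is that paragraph and a few hours of programming on data the study already collects. The interval will be slightly wider (base-case SD 0.52 against 0.50 for use-by-visit), more so under extreme missingness, and the reported improvement may be somewhat smaller. In the scenarios with equal benefit or equal missingness, use-by-visit gave the same answer as the visit-only model, so little is lost if the feared pattern is absent.
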